---

## A List of Abbreviations

Co-I	Co-Investigator
EDs	Eating Disorders
NIH	National Institute of Health
PAU	Palo Alto University
PSU	Pennsylvania State University
PI	Principal Investigator
UM	Regents of the University of Michigan
WUSM	Washington University School of Medicine

## B Introduction

### A1 Study Abstract

The prevalence of mental health problems among college populations has risen steadily in recent decades, with one-third of today's college students struggling with anxiety, depression, or an eating disorder. Yet, only 20-40% of college students with mental disorders receive treatment. Inadequacies in mental health care delivery result in prolonged illness, disease progression, poorer prognosis, and greater likelihood of relapse, highlighting the need for new approaches to detect mental health problems and engage students in services.

Our interdisciplinary research team has developed a transdiagnostic, scalable, mobile health prevention and intervention platform. This platform uses population-level screening to engage college students in tailored services that address common mental health problems. This evidence-based approach to care delivery addresses comorbid mental health issues and uses personalized screening and intervention to increase service uptake, enhance engagement, and improve outcomes. Further, our service delivery model harnesses the expertise of our team of leaders in behavioral science, college student mental health, technology, and health economics, and bridges our team's work over the past 25 years in successfully implementing a population-based screening program in over 160 colleges and demonstrating the effectiveness of Internet-based programs for targeted prevention and intervention for anxiety, depression, and eating disorders in over 40 colleges. We propose to test the impact of this mobile mental health platform for service delivery in a large-scale trial across 20 colleges. Students who screen positive or at high-risk for clinical anxiety, depression, or eating disorders

---

(excluding anorexia nervosa, for which more intensive medical monitoring is warranted), which account for a substantial proportion of the mental health burden on college campuses, and who are not currently engaged in mental health services (N=7,884; of 146,000 initially screened) will be randomly assigned to: 1) intervention via the mobile mental health platform; or 2) referral to usual care (i.e., campus health or counseling center). Our comprehensive mental health care platform can yield clinical benefit to students, appeal to university stakeholders, minimize barriers to implementation sustainability on campuses, and produce an economic return on investment compared to usual care. This population-level approach to service engagement has the potential to improve mental health outcomes for the 20+ million students enrolled in U.S. colleges and universities.

## ***A2 Primary Hypothesis***

The mobile mental health platform will yield substantially higher and earlier uptake of services compared to referral to usual care.

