## **C Study Objectives**

### ***C1 Study Aims***

Our study aims are as follows:

- 1) Aim 1: Examine uptake (i.e., individuals beginning treatment) of the mobile mental health platform compared to referral to usual care.
- 2) Aim 2: Evaluate the effectiveness of the mobile mental health platform, compared to usual care, in (2a) reducing the number of individuals with mental health disorders (primary outcome); (2b) reducing disorder-specific symptoms (secondary outcome); and (2c) improving quality of life and functioning (secondary outcome).
- 3) Aim 3: (3a) Examine if the mobile intervention changes targets previously found to be associated with outcomes, both transdiagnostic (i.e., decreased dysfunctional cognitions, increased use of CBT skills) and disorder-specific (i.e., reduced avoidance for anxiety, increased behavioral activation for depression, reduced dietary restraint and weight/shape concerns for EDs); (3b) determine if changes in targets are associated with clinical benefit; and (3c; exploratory) identify other putative mediators of change (e.g., early engagement in help services, rapid response), (3d; exploratory) within-mobile program predictors of outcome (e.g., sessions completed), and (3e; exploratory) treatment moderators.
- 4) Aim 4 Evaluate stakeholder-relevant outcomes: (4a) costeffectiveness; (4b) students' academic performance; and (4c) attitudes.

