## **2.c Adverse Event Reporting Period**

## **2.d Post-study Adverse Event**

## ***E3 Study Outcome Measurements and Ascertainment***

Study outcomes includes the following:

- Reducing the number of individuals with mental health disorders.
- Reducing disorder-specific symptoms
- improving quality of life and functioning

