## **F Statistical Plan**

### ***F1 Sample Size Determination and Power***

Sample size was based on achieving greater than 80% power to detect minimally meaningful differences in primary and secondary outcomes. We will include 20 colleges with approximately equal numbers of participants per campus, and approximately 3,154 high risk and 3,154 clinical participants with complete follow-up data. All power estimates were derived from Monte Carlo simulations (a gold standard in power estimation). For all analyses, power estimation is based on an effect size of .2 (i.e., for the primary

---

outcome, a differential change of .2 in the treatment vs. control group; for moderator analyses, effect size was .2 for each moderation effect; for mediator analyses, each pathway within the mediation was estimated at .2). We thus have power to detect smaller differences than we anticipate based on assumptions; this extra power is important, given that smaller differences would still be clinically meaningful at a population scale, particularly considering the modest cost of this online intervention. Power for all secondary outcomes was also estimated within the Monte Carlo simulation using all moderators within the same model; and all mediators within the same model targeting a .2 effect size, reflecting a conservative approach to power calculation and model estimation. Results of the Monte Carlo simulations suggested we had greater than 90% power to detect all primary outcomes and greater than 80% power to detect all secondary outcomes.

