## ***F3 Analysis Plan***

To evaluate efficacy of the mHealth platform vs. usual care, in engaging participants (Aim 1) we will use hierarchical logistic regression to examine uptake (i.e., individuals beginning any sort of treatment). Outcome will be at least one session of mental health services use (either online or in-person) assessed at 6 weeks, 6 months, and 2 years. Using hierarchical logistic regression, we will also examine efficacy in reducing or preventing number of students with mental health disorders (i.e., a positive screen for at least one of anxiety, depression, or ED as the outcome reflecting a "clinical case") assessed at 6 weeks, 6 months and 2 years, with a primary endpoint of 2 years. This allows for a single, universal outcome applicable to everyone in the study. Both logistic regression models will include random intercepts for colleges and for students nested within colleges, and account for repeated assessments within students, and will estimate the following fixed effects: main effect of time (coded as a factor variable, including baseline, 6-weeks, 6-months, and 2 years), treatment condition, and two-way interaction between time and treatment condition.

To evaluate reduction in disorder-specific symptoms (Aim 2b) and improvement in quality of life (Aim 2c), multilevel models will be used. Analyses of symptom change will be conducted within each clinical disorder subgroup separately with relevant symptoms as the response variables. We will also use a z-score to standardize primary symptom measures to obtain an estimate for a unified intervention effect. All symptom models will include random intercepts for colleges and for students nested within colleges, account for repeated assessments within students, and will estimate the following fixed effects: main effect of time, treatment condition, and two-way interaction between time and treatment condition. Parameter estimates from these models will allow separately

---

comparing change between arms from pre to 6 weeks, pre to 6 months, and from pre to 2-year follow-up. Each model will use dummy-coded factor terms as a stringent test of the treatment to ensure that: 1) treatment was associated with significantly greater change from pre to post than the control group; and 2) gains made in treatment at 6 weeks are maintained and significantly greater than baseline at each follow-up.

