
Analyses for Aim 4: Economic evaluation analyses (Aim 4a) were designed to provide information for stakeholders considering implementing the mobile platform^217. As such, analyses will be conducted from the payer's perspective to reflect opportunity cost for the payer. We will use TreeAge software, taking a multistep approach. Overall, the model will be evidence-based and fully validated using study data. A decision analytic

---

model using a microsimulation approach will be used to provide the most flexibility for testing model assumptions and provide clear evidence to decision-makers concerning reliability of results. Internal validation of the model will be conducted by comparing outcomes of participants whose data were used to construct the model to their predicted outcomes. Model fit will be tested using the R^2 statistic for continuous data and the chi-squared statistic for categorical data. External validity will be tested by comparing the model's predicted outcome to actual for participants who were "excluded" from the model-building process. The outcome of interest is the net benefit of the intervention compared to usual care at 2 years. Sensitivity of the decision model to the assumptions, including time frame, discount rate, and perspective, will be thoroughly tested using deterministic and probabilistic sensitivity analyses. We will also calculate incremental cost-effectiveness ratios, corresponding to the incremental difference (intervention vs. control) in costs divided by the incremental difference in the primary outcome, the number of clinical cases at 2-year follow-up. Monte Carlo simulations and cost-effectiveness acceptability curves will be used to present uncertainty around this estimate. Academic outcomes (Aim 4b) will be analyzed using the methods described for the primary outcomes under Aim 1. Academic outcomes will also be included into cost analyses, by translating drop-outs from college into losses in tuition (for institutions) and losses in lifetime expected productivity. Stakeholder attitudes (Aim 4c) will be assessed for variation using descriptive statistics, and will be used to predict intention to adopt the platform using ordered probit regressions (with Likert categorical variables corresponding to intention to adopt).

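### The primary hypothesis is uptake but the labelled primary outcome is 2-year caseness, and no stated alpha, test order or main uptake time point settles which result decides the trial

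*Combined protocol and SAP*

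**What the plan says.** The combined protocol and SAP describes what is primary in several places.

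- **A2 Primary Hypothesis** has one sentence: "The mobile mental health platform will yield substantially higher and earlier uptake of services compared to referral to usual care". Caseness is not mentioned.
- **C1 Study Aims** gives the label to Aim 2a: "reducing the number of individuals with mental health disorders (primary outcome". Aim 1, uptake, has no label.
- **F3 Analysis Plan** says caseness is "assessed at 6 weeks, 6 months and 2 years, with a primary endpoint of 2 years". The economic text for Aim 4a agrees: "the primary outcome, the number of clinical cases at 2-year follow-up".
- **F3, on academic outcomes (Aim 4b)**, says these will be analysed "using the methods described for the primary outcomes under Aim 1". Aim 1 is uptake.
- **F1** uses the plural, claiming "greater than 90% power to detect all primary outcomes".
- **E3** opens with "Study outcomes includes the following" and lists only caseness, symptoms, and quality of life and functioning.

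F3 defines uptake as at least one session of online or in-person services, assessed at 6 weeks, 6 months and 2 years, without naming a main time point. Uptake and caseness share one model form: time as a factor, treatment, and their interaction. The contrast that decides uptake is not named. Sections F1 to F4 give no significance level, test order, multiplicity rule or definition of trial success. The word hierarchical in F3 describes the regression model, not a testing hierarchy.

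**The concern.** A reader cannot tell from the text whether uptake or 2-year caseness decides the trial. The two could plausibly diverge. Under D1 the intervention arm is sent a direct link to the online programme, while controls receive a recommendation and a list of resources, and one online session is enough to count as uptake. Uptake could easily favour the platform while caseness at 2 years shows nothing. Under A2 that result confirms the primary hypothesis; under C1 and F3 it misses the primary outcome. The choice of headline would then be open after the results are known.

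The uptake claim is also loosely defined. It has three candidate time points, and the assertion that uptake will be earlier has neither a chosen time nor a time-to-event analysis behind it. If uptake and caseness are both treated as confirmatory with no shared rule, the chance of at least one false primary claim exceeds the level of a single test.

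**Working it through.** **1. The plan's own figure.** The only related figure is F1's power of more than 90% for the primary outcomes at an effect size of .2. It cannot be reproduced exactly, because the simulation's alpha, base rates, clustering and effect scale are not given. As a plausibility check, take F1's 3,154 + 3,154 = 6,308 completers, assume 1:1 allocation (3,154 per arm) and two-sided 5%, and ignore clustering. A standardised difference of .2 gives power above 99.9%, which is consistent with F1. If .2 is a log odds ratio, power is 87% to 98% for control rates of 20% to 60%. No family-wise error figure is stated anywhere.

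**2. Counting the tests.**
- Caseness: one test, at 2 years (F3).
- Uptake: one test if the 2-year endpoint is taken to govern it too; three if each assessment time counts.
- Total: at least 1 + 1 = 2, at most 3 + 1 = 4.

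**3. Family-wise error when nothing truly differs.** No alpha is stated, so two-sided 0.05 per test is assumed. For k independent tests the error is 1 − (1 − 0.05)^k.
- k = 2: 1 − 0.95² = 1 − 0.9025 = 9.75%.
- k = 4: 1 − 0.95⁴ = 1 − 0.8145 = 18.5% (Bonferroni bound 4 × 5% = 20%).

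**4. Allowing for correlation.** The three uptake measures come from the same students, so independence is unrealistic. A multivariate normal simulation (2,000,000 draws) of the four-test case gave:

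| Correlation among uptake tests | Correlation with caseness | Error, two-sided | Error, false claims for the platform only |
|---|---|---|---|
| 0 | 0 | 18.5% | 9.6% |
| 0.3 | 0 | 17.9% | 9.1% |
| 0.5 | 0.3 | 16.4% | 8.2% |
| 0.7 | 0.3 | 15.0% | 7.5% |
| 0.9 | 0.3 | 12.6% | 6.3% |

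The benchmark for one named test is 5% two-sided, or 2.5% in the platform's favour. The correlations are assumptions; the documents give none.

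**5. If uptake truly differs.** Rejecting the uptake null is then correct and adds no false positive. The single 2-year caseness test keeps its own 5% error. What remains is the question of which result counts as success.

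**6. With a declared order.** If the second test is made only when the first is significant, a false claim when nothing differs requires the first test to reject falsely, so the family-wise error is 5%. If the first effect is real, only the second test can err, again at 5%. No alpha is split.

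**The case against.** The strongest reply is that the primary outcome is already identifiable. C1 labels it, F3 gives it a time point and presents it as one outcome that applies to everyone, the Aim 4a text repeats it, and F1 uses the singular when it sets out the .2 effect. On this view A2 is a loosely worded heading, and the Aim 4b phrase is a cross-reference to methods. C2 also treats use of the platform and its effectiveness as separate questions, and whether separate questions must share an error rate is partly a design choice. This stands in part: it is why the repair is easy and why caseness is the natural choice. It does not remove the conflict, because a section titled Primary Hypothesis names a different endpoint and nothing ranks uptake against caseness.

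Three stronger readings are tempting and are not supported.

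- A reader might infer that the plan allows success on any one of four tests. No section says that a single success suffices. The documents are silent on a success rule, so they do not prevent the claim, which is a narrower point. Four is also an upper bound, since F3 describes one repeated-measures model for uptake.
- A reader might take 18.5%, or even 9.75%, as the trial's actual error rate. Both need an assumed alpha, independence and no effect on either outcome. Given how uptake is defined, no effect on uptake is unlikely.
- A reader might treat the absence of uptake from E3 as a decision to drop it. E3 also omits targets, academic outcomes and costs, and the schedule in E2 marks treatment utilisation as a treatment outcome at 6 weeks, 6 months and 2 years. E3 is an incomplete list.

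**Conclusion.** The concern holds as an inconsistency that should be resolved. A2 makes uptake the only primary hypothesis, while C1 and F3 make 2-year caseness the primary outcome. The references to primary outcomes under Aim 1 and to several primary outcomes add to the conflict. Uptake lacks a main time point, its earliness lacks a test, and no alpha or order is stated.

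The main consequence does not depend on any error rate: positive uptake with null caseness could be reported in two opposite ways. The error inflation is conditional. With two-sided 5% per test and no true effect on either outcome, it is 9.75% for two independent tests. If every uptake time counts, it is at most 18.5% for four independent tests, or about 12.6% to 17.9% with correlations of 0.3 to 0.9 among the uptake tests and 0 to 0.3 with caseness.

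**What to change.** Before outcome data are examined:

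1. State the significance level and name 2-year caseness as the single primary outcome, as C1 and F3 already do.
2. Name uptake at one stated time point as the first key secondary outcome. Six weeks is one option and would give the claim of earlier uptake a defined test.
3. Test uptake at two-sided 5% only if 2-year caseness is significant at two-sided 5%.
4. If the sponsor wants uptake to lead, declare the reverse fixed order instead: uptake at the stated time, then 2-year caseness. Either order controls the error; one must be chosen and written down.
5. Align A2, E3, F1 and the Aim 4b sentence in F3 with the choice.

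The cost is wording. No alpha is split and no participants are added. The real downside is that the second claim depends on the first test succeeding: with caseness first, a null caseness result leaves uptake without a confirmatory claim, and with uptake first the reverse applies.

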## **B Background**

### ***B1 Prior Literature and Studies***

Prevalence of mental health problems among college students has risen steadily in recent decades. In national epidemiologic studies, past-year prevalence of mood and anxiety disorders was 11% and 12%, respectively, and 9% of college students screened positively for an eating disorder (ED). Among students with probable disorders, only 20-40% received treatment, and this number was even lower among students of color and those from low-income families. With over 20 million people enrolled in U.S. postsecondary education, we can infer an extremely large treatment gap—there are at least 6.5 million college students with mental disorders, and at least 4 million college students with untreated mental disorders. Early intervention is particularly important during college ages of 18-24, when mental illnesses account for the largest burden of any disease. Untreated symptoms become more frequent, severe, and persistent over time. Students often have difficulty getting appropriate health care, which can have lasting consequences on functioning, physical health, suicidality, social relationships, and educational attainment. Although many campus counseling and health centers have increased their capacity to provide services, there remain major limitations to access and delivery of mental health services in college populations. For students, important barriers include lack of problem recognition, lack of time, lack of urgency to seek services, and stigma. Increasing the number of providers, by itself, neither addresses the large number who wait until they reach a crisis level to seek mental health support, nor alleviates stigma or campus leaders' concerns about continuing to pour more resources into services without appreciable slowing in demand. These factors highlight the need for a more efficient, proactive, and accessible service delivery model for managing mental health in college student populations through combined targeted prevention and intervention.

---

## ***B2 Rationale for this Study***

mHealth technologies have potential to improve mental health care on college campuses by overcoming treatment barriers and increasing efficiency. Such interventions can offset in-person clinical demands, increase access, enhance treatment precision, and reduce costs. Mobile technologies are efficacious for screening and treatment of anxiety, depression, and EDs across settings and populations, including in college students for whom smartphone use is ubiquitous, with high acceptability given their convenience and anonymity. However, these interventions have been primarily delivered independently. A key challenge is delivering these technologies effectively and in combination at a population level. Such an approach would link screening with intervention, maximize engagement, and address comorbid problems.

---

## **C Study Objectives**

### ***C1 Study Aims***

Our study aims are as follows:

- 1) Aim 1: Examine uptake (i.e., individuals beginning treatment) of the mobile mental health platform compared to referral to usual care.
- 2) Aim 2: Evaluate the effectiveness of the mobile mental health platform, compared to usual care, in (2a) reducing the number of individuals with mental health disorders (primary outcome); (2b) reducing disorder-specific symptoms (secondary outcome); and (2c) improving quality of life and functioning (secondary outcome).
- 3) Aim 3: (3a) Examine if the mobile intervention changes targets previously found to be associated with outcomes, both transdiagnostic (i.e., decreased dysfunctional cognitions, increased use of CBT skills) and disorder-specific (i.e., reduced avoidance for anxiety, increased behavioral activation for depression, reduced dietary restraint and weight/shape concerns for EDs); (3b) determine if changes in targets are associated with clinical benefit; and (3c; exploratory) identify other putative mediators of change (e.g., early engagement in help services, rapid response), (3d; exploratory) within-mobile program predictors of outcome (e.g., sessions completed), and (3e; exploratory) treatment moderators.
- 4) Aim 4 Evaluate stakeholder-relevant outcomes: (4a) costeffectiveness; (4b) students' academic performance; and (4c) attitudes.

